#### **Objective 4: Assess participant experience and optimize outcome measures across sites.**

Well-developed content themes with data saturation emerging from feedback interviews will provide information on acceptability, impact of assessments, protocol and intervention fidelity, and equivalence of these markers across sites. Benchmark sensitivity and responsiveness values will determine the most sensitive and responsive measures relative to all study outcomes, versus a significance testing approach in which standardized/conventional threshold values are used to make decisions regarding significance. Sensitivity and responsiveness information will determine which outcomes are most impacted by MBRT for retention in a future full-scale multi-site efficacy trial. Benchmarks for equivalence across sites will be evidenced by: a) qualitative themes that suggest experiential continuity across sites, and b) equivalence in outcome measure response distributions, reliability estimates, and intraclass correlations.

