The target population for our study is LEOs working in urban settings in the United States. LEOs will be recruited from Portland Police Bureau (PPB), Albuquerque Police Bureau (APB), and Madison Police Department (MPD). PPB employs 966 full-time, active duty officers, serving approximately 603,106 citizens in the Greater Portland Metropolitan Area; women and racial/ethnic minorities represent 16% and 16%, respectively. APD employs 921 full-time, active duty officers, serving approximately 907,301 citizens in the Greater Albuquerque Metropolitan Area; women and racial/ethnic minorities represent 16% and 47%, respectively. MPD employs 486 full-time, active duty officers, serving approximately 258,054 citizens in the Greater Madison Metropolitan Area; women and racial/ethnic minorities represent 28% and 21%, respectively. We will make concerted efforts to recruit a target final sample comprising  $\geq 16\%$  women and  $\geq 16\%$  racial/ethnic minorities in Portland,  $\geq 16\%$  women and  $\geq 35\%$  racial/ethnic minorities in Albuquerque,  $\geq 25\%$  women and  $\geq 20\%$  racial/ethnic minorities in Madison.

We will recruit 104 participants. Using a 2:1.5:1 randomization allocation ratio for MBRT, SME, and NIC conditions, respectively, across the three study sites, 47 participants will be randomized to MBRT; 35 to SME; and 22 to NIC. Our sample size is based on feasibility trial recommendations suggesting 12-25 participants per arm to optimize estimation of group means and variability without oversampling in terms of diminishing returns in parameter estimation, and to provide reasonably precise information in terms of confidence intervals around retention rates.

If we do not get an adequate response from either of the two departments, we will expand recruitment to neighboring police departments in the Greater Portland Metro and/or Albuquerque Metro areas.

All data collection will happen remotely, either online or via home-based collection and mail (for dried blood spot samples).

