to obtain more accurate (i.e., unbiased)  $F$ -values, we will include study site and gender, as covariates in all ANOVA analyses (i.e., perform a one-way between-subjects Analysis of Covariance for each outcome). Assessing relative efficiency entails generating  $F$ -values for comparison purposes and does not require determining whether the group differences are significant; however, adjusting for non-ignorable clustering will allow us to avoid deviation from a type I error rate of .05 and calculate  $F$ -values that most precisely reflect group differences for each outcome. Responsiveness to change will be assessed, in part, by comparing standardized mean responses, which will not require conducting an inferential test and therefore will not be impacted by type I or type II error rates. To assess responsiveness to change, we will also calculate partial correlations with a global impression of change measure and residualized change scores for each self-reported outcome, adjusting for variability due to gender and study site. Just as for our relative efficiency assessment, examination of partial correlations will not entail significance testing, but instead generating correlation coefficients for comparative purposes; however, we will partial out variability due to gender and study site to obtain precise (i.e., unbiased) estimates of covariance between a global impression of change measure and self-report outcomes.

Based on our recent R21 study (R21AT008854), in which we had an overall attrition rate of 20% across all study arms, we predict an overall attrition rate of 20% across our three study arms.

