To calculate the relative efficiency of MBRT versus NIC, we will conduct one-way, between-subject ANCOVAs with MBRT vs. NIC as the independent variable, each outcome variable at post-training as the dependent variable, and gender and study site as covariates. Again, we will also conduct ANOVAs using the same independent and dependent variables to ensure all inferential tests are conducted and identify any potential Type II Errors among the ANCOVAs. We will then divide the *F*-statistic for each behavioral, physiological, and self-report outcome by the largest *F*-statistic among these analyses; again, the larger the number, the more sensitive the outcome is to MBRT relative to the no-treatment control group. These sensitivity analyses will allow assessment of which behavioral, physiological, and self-report outcomes are most sensitive to MBRT.

Responsiveness to change across time will be assessed in the MBRT arm for behavioral, physiological, and self-report outcomes by: 1) calculating and comparing standardized mean responses (SMR) for outcomes by subtracting the baseline mean response for each outcome from the post-intervention mean response for that outcome, and dividing by the standard deviation of change for that outcome; 2) calculating and comparing partial correlation coefficients (adjusting for study site and gender) between a global impression of change measure that captures the subjective experience of changes in stress, job performance, and resilience at post-intervention and residualized change scores (baseline to post-intervention) for each self-report outcome. For both SMR values and correlation coefficients, the higher the absolute value, the more responsive the outcome is to change across time in the MBRT arm. We will conduct additional correlation analyses using the same variables without adjusting for study site and gender to identify any potential Type II Errors among the partial correlations.

In addition, we will examine data for any indications of systematic site differences. Using baseline data (where sample size will be greatest) and pooling arms, since no treatment differences are expected at baseline, distributions of standardized responses on outcome measures will be summarized, graphed, and compared across sites. Key parameters, reliability

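### Outcomes are ranked on standardized mean responses and correlations with no measure of uncertainty, although 38 to 47 MBRT officers cannot reliably separate measures that differ modestly in responsiveness

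*Combined protocol and SAP*

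**What the plan says.** Section 9.2 says that responsiveness will be judged partly by comparing SMRs, a comparison that "will not require conducting an inferential test and therefore will not be impacted by type I or type II error rates". It adds that the partial correlations involve no significance testing either.

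Section 9.6 (Quantitative) defines the SMR within the MBRT arm as the change in mean from baseline to post-intervention, "dividing by the standard deviation of change for that outcome". The second statistic is the partial correlation between a global impression of change and the residualized change in each self-report outcome. For both, the rule is that "the higher the absolute value, the more responsive the outcome is to change across time in the MBRT arm".

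Section 1.1, Objective 4, states the use: "Sensitivity and responsiveness information will determine which outcomes are most impacted by MBRT for retention in a future full-scale multi-site efficacy trial". Section 9.1 says the results will set the primary and secondary outcome categories of that trial. Objective 4 puts benchmark values in place of significance thresholds but gives no number. Section 9.1 names confidence intervals as a general aim. Neither 9.2 nor 9.6 attaches one to an SMR, a correlation or a rank.

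**The concern.** Leaving out a test does not leave out sampling error. Choosing the outcomes with the largest SMRs or correlations is a decision made on estimates. It can pick the wrong outcome, and the value of the one picked is biased upward because it was picked for being large. Section 9.2 reads as if the comparison needed no allowance for error, and 9.6 provides none. Section 9.6 is also at odds with 9.2: it repeats the correlations without covariates to look for Type II errors, although 9.2 says they are not tested.

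At stake is which measures go into the efficacy trial. Without intervals, a reader of the ranking cannot tell a real difference in responsiveness from noise.

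**Working it through.** **Inputs from the documents.** Section 3: "We will recruit 104 participants", in the ratio 2:1.5:1, giving "47 participants will be randomized to MBRT; 35 to SME; and 22 to NIC". Section 9.2: "we predict an overall attrition rate of 20% across our three study arms". Section 9.6 lists seven self-report outcomes, four biomarkers and a use-of-force composite, so at least 12 candidates. The documents give no true SMRs and no correlations between outcomes; those below are assumptions.

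**The plan's own figure.** 104 × 2/4.5 = 46.2, 104 × 1.5/4.5 = 34.7 and 104 × 1/4.5 = 23.1, against 47, 35 and 22 stated. These agree to within about one officer per arm.

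**Evaluable MBRT officers.** 47 × 0.80 = 37.6, about 38, with full attrition, and 47 with none.

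**Precision of one SMR.** SE = √(1/n + d²/(2n)). At d = 0.3:
- n = 38: √(0.02632 + 0.00118) = 0.166; 95% half-width 1.96 × 0.166 = 0.33, interval −0.03 to 0.63.
- n = 47: √(0.02128 + 0.00096) = 0.149; half-width 0.29, interval 0.01 to 0.59.

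**Precision of one partial correlation.** Fisher's z with three covariate terms (two for site, one for gender) has SE = 1/√(n − 6). For an assumed r of 0.3 (z = 0.310):
- n = 38: SE = 1/√32 = 0.177, interval −0.04 to 0.58.
- n = 47: SE = 1/√41 = 0.156, interval 0.00 to 0.55.

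**Difference between two SMRs in the same officers.** With correlation ρ between change scores, SE = √{[2 + d₁²/2 + d₂²/2 − 2(ρ + d₁d₂ρ²/2)]/n}. For d₁ = 0.5 and d₂ = 0.3, the 95% half-widths are:

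| ρ | n = 38 | n = 47 |
|---|---|---|
| 0 | 0.47 | 0.42 |
| 0.3 | 0.40 | 0.36 |
| 0.5 | 0.34 | 0.30 |
| 0.7 | 0.27 | 0.24 |

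All exceed the true difference of 0.2.

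**The ranking rule.** I simulated 20,000 trials per setting with 12 outcomes, true SMRs evenly spaced from 0.1 to 0.5 and normal change scores with common correlation ρ. Each trial picked the largest absolute SMR.

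| n | ρ | Top-ranked is truly best | True best is in top three | Overstatement of top SMR |
|---|---|---|---|---|
| 38 | 0.2 | 31% | 67% | 0.22 |
| 38 | 0.3 | 32% | 69% | 0.20 |
| 38 | 0.4 | 34% | 71% | 0.18 |
| 47 | 0.2 | 33% | 70% | 0.19 |
| 47 | 0.3 | 35% | 72% | 0.17 |
| 47 | 0.4 | 36% | 75% | 0.16 |

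If all 12 outcomes truly have an SMR of 0.30 (n = 38, ρ = 0.3), the expected largest and smallest observed values are 0.55 and 0.08.

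**Dependence on the gap.** Take n = 38, one outcome better than eleven others at 0.3, and ρ from 0 to 0.7. The best one ranks first in 20–31% of trials for a gap of 0.1, 34–65% for 0.2, 54–89% for 0.3 and 85–100% for 0.5.

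**The case against.** **The sentence is literally true.** Type I and Type II errors belong to tests, and no test is run on SMRs. A reader might infer that 9.2 makes a false statement, or claims that SMRs are free of sampling error. It says neither. What stands is that the sentence serves as a reason to give no uncertainty, so rewording is enough.

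**The plan does not crown one winner on one statistic.** It looks for several measures. It also uses relative efficiency against SME and against NIC, correlations with perceived change, and a qualitative check. This stands: the chance of picking the single best is a stricter yardstick than the plan's decision. In the simulation at n = 38, the outcome ranked first has a true SMR averaging 0.43 to 0.44 against a best of 0.50, so a wrong pick often costs little. But the other quantitative criteria are also read as bare point values, so they do not supply the missing uncertainty.

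**The next trial will be sized on an inflated SMR.** A reader might infer this. Section 9.2 names means, variability and intraclass correlations as inputs, not the within-arm SMR. The harm arises only if a selected outcome's observed effect is used.

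**This is a feasibility trial.** Agreed; nothing here calls for a power calculation or more officers. Estimating uncertainty fits the aim in 9.1.

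**The sample size is not settled.** The 20% is overall attrition, while SMRs use post-intervention data, and 9.3 allows multiple imputation; hence the range of 38 to 47. These are officers retained, not treatment completers, which the protocol defines by attendance. The 15% missing data that Objective 2 allows among active participants could instead lower n to 37.6 × 0.85 = 32, with a half-width of 0.35 at an SMR of 0.3.

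**Conclusion.** The point holds as an omission in the analysis plan. The SMRs and partial correlations that help choose future outcomes are ranked with no statement of uncertainty, and 9.2 gives the absence of a test as the reason. An SMR near 0.3 is known only to about ±0.29 to ±0.33. Under the assumed spread of true values, the top rank is right in about 31 to 36% of trials, and the top SMR is too large by about 0.16 to 0.22.

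It does not follow that the ranking is useless at this sample size. True gaps near 0.5 would usually be found, and the best measure is among the top three in about 67 to 75% of the simulated trials. The documents do not say which situation applies; the intervals would show it. The calculations treat officers as independent. MBRT is given in groups of 10 to 13 (Section 5.1) and 9.6 declines to adjust for intraclass correlation, so real precision may be worse.

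**What to change.** 1. Reword the sentence in 9.2, for example: *SMRs and partial correlations are compared without significance tests. They carry sampling error, and selecting the largest of several overstates it; both are reported with measures of uncertainty.*
2. Add to 9.6 a bootstrap that resamples officers with all their outcomes together. Report 95% intervals for each SMR, each partial correlation, and the pairwise differences or ranks. If data are imputed, build the imputation into the procedure.
3. Respect the MBRT groups where feasible. With 47/13 = 3.6 to 47/10 = 4.7, there are only about four or five groups, so resampling whole groups may be unstable. If officers are resampled instead, say that the intervals ignore grouping and may be too narrow.
4. Treat outcomes as tied with the top one when the interval for the difference includes zero, and choose among them on the plan's other stated criteria.
5. If a selected outcome's observed effect is used to size the next trial, use a shrunken or selection-corrected value. The raw maximum is too large, and the lower limit is not usable: at an SMR of 0.3 and n = 38 it is −0.03.

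The cost is a little more analysis and a less decisive ranking. No new data or visits are needed.

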### **9.2.1 Treatment Assignment Procedures**

Randomization will be stratified first by study site, and then within study site by gender. We will employ a permuted-block randomization procedure, stratifying by gender, to assign participants to study arms. We will employ this randomization procedure to: 1) be able to optimize the study procedures we plan to use in a future fully-powered efficacy RCT, 2) obtain parameter estimates that reflect the causal impact of MBRT on outcomes, 3) assess measure sensitivity and responsiveness in a way that reflects the causal impact of MBRT on participants, and 4) ensure balance within strata and across study arms.

Using procedures piloted in our R21 (R21AT008854), following baseline assessment, study staff not involved in data collection will randomly assign participants to condition using SPSS and REDCap. The study statistician will create an allocation table using SPSS, and upload it to REDCap, which will be used to implement the randomization procedure at each site. All trial randomization codes will be stored within REDCap, which is a secure (HIPAA-compliant) internet-based survey and data management software system housed on a secure server at Oregon Health and Science University.

This study does not meet criteria for a double- or triple-blinded RCT, as the study participants will be aware of their intervention assignment. To limit possible bias, the participants will be asked to not reveal their treatment assignment to data collection staff. Masking will be maintained by compartmentalizing study staff to a certain category of tasks that will prevent the study staff analyzing data from interacting with study participants and knowing participant names or any other personally identifying information, the study staff involved in implementing the intervention from being involved in data collection and analysis, the study staff involved in randomizing study participants and informing them of their study arm assignment from being involved in intervention implementation and data collection, and the study staff involved in data collection from knowing study arm assignment. Only study staff involved in recruitment activities will have access to both participant names and unique ID codes. The study statistician will monitor protocol fidelity around masking by maintaining contact with study staff involved in intervention implementation, data collection, and randomization to ensure that masking is maintained and identify any protocol violations. If a protocol violation occurs around masking, the study statistician will consult with the MPIs to identify the nature of the violation, the reason for the violation, and potential remediation plans. The study statistician will then implement the remediation plan by working with relevant study staff. Our study protocol does not require unblinding at any point during the study phase; however, if an unforeseen situation requires that unblinding becomes necessary, the study statistician, in consultation with the MPIs, would coordinate and implement the unblinding. If additional study staff beyond the statistician and MPIs are necessary to implement the unblinding, the statistician will only enlist the help of study staff who are absolutely necessary to implement the unblinding. If the unblinding compromises a study staff's ability to engage in his/her/their assigned task, we will replace that study staff member.

### **9.3 Definition of Populations**

Our sensitivity and responsiveness analyses will utilize an ITT approach. If attrition occurs, the study statistician will review the reasons for withdrawal to determine if missing data are missing completely at random (MCAR), missing at random (MAR), or missing not at random (MNAR). If data are MCAR, then we will use a complete-case approach to estimate parameters and conduct sensitivity and responsiveness analyses. If missing data are MAR or MNAR, we will employ a multiple imputation approach to impute data before estimating parameters and conducting sensitivity and responsiveness analyses. We will also estimate parameters and conduct sensitivity and responsiveness analyses using a complete-case approach for comparison purposes.

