Participants randomized to the NIC condition will not receive any intervention, but will participate in the same assessments as the two active intervention conditions (i.e., at baseline, post-intervention, 3- and 6-month follow-up). Assessment times will be yoked to those of the two active intervention conditions.

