#### **6.2.5 Completion/Final Evaluation**

The final evaluation is the 6-month followup. See above for assessments.

Study coordinator will contact any participants who discontinue the intervention to identify reason for early termination (e.g., illness, not finding the intervention beneficial, schedule change). In the event a participant discontinues due to an intervention-related adverse event, study staff will continue to follow-up with the participant until the issue is resolved.

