When a participant drops out, we will attempt to obtain information from that LEO regarding the reason for withdrawal. This information will allow us to determine the nature of the missing data (i.e., missing completely at random, missing at random, missing not at random) for analytic purposes; assess whether the withdrawal is due to a protocol violation and if the LEO experienced an AE due to the intervention (if the LEO is in the MBRT or SME arm); and obtain information that could inform future program modifications (e.g., increase the flexibility of program delivery, reduce participant burden, etc.). All protocol violations will be handled by having the Co-PIs meet with relevant study staff to identify the nature of the violation, the reason for the violation, and potential remediations; the Co-PIs will then work with all relevant study staff to implement a remediation plan and decide on a timeframe for re-assessing the procedure to ensure the violation is not re-occurring.

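### Section 9.3 lets withdrawal reasons choose the missing-data analysis, leaves an MCAR label with complete cases only, and states no MNAR assumption

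*Combined protocol and SAP*

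**What the plan says.** Section 9.3 adopts an intention-to-treat approach. Once attrition occurs, "the study statistician will review the reasons for withdrawal to determine if missing data are missing completely at random", at random, or not at random. Each label then leads to an analysis. For the first: "If data are MCAR, then we will use a complete-case approach to estimate parameters and conduct sensitivity and responsiveness analyses". For the other two: "If missing data are MAR or MNAR, we will employ a multiple imputation approach to impute data before estimating parameters". The section ends by adding analyses "using a complete-case approach for comparison purposes". It gives no criteria for assigning the label, no imputation model, no number of imputations, and no assumption about how unseen values might differ from observed ones. Section 9.6 adds nothing on missing data.

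Section 9.2 rests on the same idea. When someone drops out, "we will attempt to obtain information from that LEO regarding the reason for withdrawal", and "This information will allow us to determine the nature of the missing data". That section predicts 20% attrition overall. Objective 2 in Section 1.1 separately expects up to 15% missing data from active participants who omit or decline measures.

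The estimates affected are those for which Sections 9.1 and 9.6 say the trial is run: group means, variability and confidence intervals; F-values at post-training for MBRT against SME and against NIC; and, within MBRT, standardized mean responses (SMRs) and correlations with a global change rating.

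**The concern.** The rule asks withdrawal reasons to do something they cannot do. MAR and MNAR differ in whether missingness depends on the unseen values, given what was observed, and a stated reason does not settle that. The reasons may also be unavailable, since staff only undertake to try to get them. A skipped measure from someone still in the study has no withdrawal reason at all. The label is assigned after the losses have occurred, without criteria, and it determines which results are produced.

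The branches have different weaknesses. Under an MCAR label the added comparison is again complete-case, so imputation is never run. Under a MAR or MNAR label the same undescribed imputation is used, and nothing specified would show what happens if MAR fails. At stake are the means and SMRs that will be used to choose outcomes and size the next trial; their confidence intervals would not reflect this bias.

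**Working it through.** **Inputs from the plan.** Arms of 47, 35 and 22 (Section 3); as a check, 104 × 2/4.5 = 46.2, 104 × 1.5/4.5 = 34.7 and 104 × 1/4.5 = 23.1, close to the stated sizes. Attrition of 20% overall (Section 9.2). Up to 15% missing from active participants (Section 1.1). The plan gives no figure for missing-data bias, so there is none to reproduce.

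**Assumed, not in the documents.** Baseline-to-post correlation r = 0.6; true SMR 0.40; higher scores better; loss of 20% or 10% (9 or 5 of 47 in the simulations).

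**Step 1. Missing values with no withdrawal reason.** Suppose the 15% applies to each measure. At 20% attrition, 0.15 × 0.80 = 0.12 is missing without withdrawal, out of 0.20 + 0.12 = 0.32, and 0.12/0.32 = 37.5%. At 10% attrition, 0.15 × 0.90 = 0.135 out of 0.235, or 57%. The 15% is a ceiling and the 20% is study-wide, so the 32% total is a worst case.

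**Step 2. Wrong MCAR label.** If dropouts are worse at baseline by a gap g (in SD), the complete-case post mean is too high by about loss × r × g.
- 20% loss: 0.20 × 0.6 × 0.1 = 0.012; 0.20 × 0.6 × 0.5 = 0.060.
- 10% loss: 0.10 × 0.6 × 0.1 = 0.006; 0.10 × 0.6 × 0.5 = 0.030.

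Simulation at g = 0.5 gave +0.061 and +0.033, with SMR bias of −0.044 and −0.024. Imputation on baseline was within 0.004 of zero.

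**Step 3. Departure from MAR.** If unseen values differ by delta (in SD) from what MAR predicts, the arm-mean bias is loss × delta.
- 20% loss: 0.20 × 0.25 = 0.05; 0.20 × 0.5 = 0.10.
- 10% loss: 0.10 × 0.25 = 0.025; 0.10 × 0.5 = 0.05.

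Simulation at 20% and delta ±0.5 gave imputed-mean bias of +0.096 and −0.100, against +0.098 and −0.099 for complete cases. The two analyses agree and are equally wrong.

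**Step 4. Between-arm contrast.** With equal loss and equal delta in both arms the biases cancel. With 47 against 35, 20% loss in each arm, an assumed true difference of 0.5 SD before the shift, and only MBRT dropouts 0.5 SD worse than MAR predicts, the full-data difference is 0.40; complete cases and imputation both give 0.50.

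**Step 5. Ranking by SMR.** Two outcomes with true SMRs of 0.40 and 0.45, correlation 0.3 between them, and the same dropouts. The table shows how often the weaker one ranks first.

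| Delta, weaker / stronger | 20% loss: full data → imputed | 10% loss: full data → imputed |
|---|---|---|
| 0.5 / 0.5 | 39% → 41% | 41% → 41% |
| 0.5 / 0.25 | 37% → 51% | 39% → 46% |
| 0.5 / 0 | 40% → 62% | 36% → 51% |
| 0 / 0.5 | 40% → 22% | 42% → 30% |

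**Step 6. Scale.** The sampling SD of an SMR at n = 47 is about √(1/47 + 0.40²/(2 × 47)) = 0.15.

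**The case against.** The strongest reply is that this is a 104-person feasibility trial with no efficacy hypothesis. It ranks outcomes without significance testing, and most of the biases above are smaller than sampling error. The 20% is overall attrition, and Section 1.1 ties its 80% retention target to 6 months, whereas the F-values and SMRs use data collected within 21 days of the course, so loss at that point may be lower. Randomization follows the completed baseline assessment (Sections 4.3 and 6.2.2), so baseline values exist for dropouts in every arm and a wrong MCAR label could be partly checked. Full data already misorder the two hypothetical outcomes in Step 5 about 40% of the time. All of this stands and limits the size of the point. It does not rescue the rule: no baseline comparison of dropouts and completers is planned, and no baseline comparison can detect MNAR.

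Two stronger readings are tempting. A reader might infer that NIC dropouts are never asked for a reason, because Section 6.2.5 says "Study coordinator will contact any participants who discontinue the intervention to identify reason for early termination" and Section 5.1 says "Participants randomized to the NIC condition will not receive any intervention". The documents do not support that: the commitment in Section 9.2 covers any participant who drops out, and its parenthesis about the MBRT and SME arms limits only the adverse-event question. A reader might also infer that the plan rules out an MNAR imputation. It does not; it specifies none.

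**Conclusion.** The point holds as a fault in the rule itself, with modest consequences. The wording is clear: withdrawal reasons select the analysis, an MCAR label leaves no imputed result, and MAR and MNAR share one imputation with no stated MNAR assumption. That part is held with high confidence.

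The size rests on assumed values. Dropout linked to baseline would bias complete-case means by about 0.01 to 0.06 SD at 20% loss and 0.01 to 0.03 SD at 10%, avoidably. A departure from MAR of 0.25 to 0.5 SD would bias both planned analyses by about 0.05 to 0.10 SD at 20% and 0.03 to 0.05 SD at 10%, in either direction and unseen. It would be going too far to conclude that the choice of outcomes will be wrong: equal departures leave the SMR ranking almost unchanged, and movement requires departures that differ between outcomes or, for the F-values, also between arms. The rule should be changed because the estimates it can bias are the trial's main product and the change is cheap.

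**What to change.** Delete the sorting rule and report withdrawal reasons descriptively. Then specify:

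- **Main analysis.** Multiple imputation under MAR for all randomized participants, covering both withdrawals and measures missing from active participants. Use arm, site, gender, and the baseline and available follow-up values of the outcome, in a model small enough for NIC (22).
- **Number of imputations.** At least 50. In simulations with 20 to 32% missing, imputation noise (SD) in the pooled SMR was 0.031 to 0.042 with 5 imputations and 0.010 to 0.014 with 50; for the pooled F it was 0.74 to 1.00 and 0.24 to 0.31.
- **Pooling.** Rubin's rules for the ANCOVA and ANOVA contrasts; each has one degree of freedom, so F is the squared pooled t. Average the SMRs across imputed sets. Pool the partial and unadjusted correlations on the Fisher z scale.
- **MNAR check.** A few two-sided delta shifts justified by the team, applied (a) equally to all participant-reported and biomarker outcomes and (b) to one outcome at a time, each in MBRT only and in all arms. Report whether the F or SMR ranking changes.
- **Supportive analysis.** Complete cases.

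The cost is SAP wording and scripted analysis, with no new data. There are at least 7 self-report + 4 biomarker + 1 use-of-force composite = 12 outcomes, so each setting yields at least 12 × 2 contrasts × 2 models = 48 F-values, plus 12 SMRs and the correlations. The downside is more tables, and the delta range remains a judgement.
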